5. SELECTION AND WITHDRAWAL OF STUDY POPULATION

5.1. General Study Population and Clinical Sites

Up to approximately 20 participants with symptomatic oHCM are expected to enroll in this study at up to 5 clinical sites in the United States (US).

5.2. Inclusion Criteria

Each participant must meet the following criteria to be enrolled in this study.

1. Has completed Study MYK-461-004. Prior participation in a non-interventional observational study is allowed
2. Able to understand and comply with the study procedures, understand the risks involved with participating in the study, and provide written informed consent according to federal, local, and institutional guidelines before the first study-specific procedure
3. Body weight > 45 kg at Screening
4. Has safety laboratory parameters (chemistry and hematology) within normal limits (according to the central laboratory reference range) at Screening; however, a participant with safety laboratory parameters outside normal limits may be included if he or she meets all of the following criteria:
 - The safety laboratory parameter outside normal limits is considered by the Investigator to be clinically unimportant
 - If there is an alanine aminotransferase (ALT) or aspartate aminotransferase (AST) result, the value must be $< 3 \times$ the upper limit of the laboratory reference range
 - The body size-adjusted estimated glomerular filtration rate is ≥ 30 mL/min/1.73 m²
5. Female participants must not be pregnant or lactating and, if sexually active, must use one of the following highly effective birth control methods from the Screening visit through 4 months after the last dose of investigational medicinal product (IMP).
 - combined (estrogen- and progestogen-containing) hormonal contraception associated with inhibition of ovulation or progestogen-only hormonal contraception associated with inhibition of ovulation by oral, implantable, or injectable route of administration
 - intrauterine device (IUD)
 - intrauterine hormone-releasing system (IUS)
 - bilateral tubal occlusion
 - Female participant is surgically sterile for 6 months or postmenopausal for 1 year. Permanent sterilization includes hysterectomy, bilateral oophorectomy, bilateral salpingectomy, and/or documented bilateral tubal occlusion at least 6 months prior to Screening. Females are considered postmenopausal if they have had amenorrhea for at least 1 year or more following cessation of all exogenous hormonal treatments and follicle-stimulating hormone (FSH) levels are in the postmenopausal range.

Male partners must also use a contraceptive (eg, barrier, condom, or vasectomy).

5.3. Exclusion Criteria

A participant who meets any of the following criteria will be excluded from the study.

1. Has QTcF > 500 milliseconds or any other ECG abnormality considered by the Investigator to pose a risk to participant safety (eg, second-degree atrioventricular block type II)
2. Since enrollment into Study MYK-461-004, has developed obstructive coronary artery disease (> 70% stenosis in one or more arteries) or known moderate or severe aortic valve stenosis
3. Since enrollment into Study MYK-461-004, has developed any acute or serious comorbid condition (eg, major infection or hematologic, renal, metabolic, gastrointestinal, or endocrine dysfunction) that, in the opinion of the Investigator or Medical Monitor, would pose a risk to participant safety or interfere with the study evaluation, procedures, or completion
4. Has a positive serologic test at Screening for infection with human immunodeficiency virus, hepatitis C virus, or hepatitis B virus
5. Since enrollment into Study MYK-461-004 has developed clinically significant malignant disease
6. Is taking prohibited concomitant medications (see [Section 7.7.3](#)); background therapy on beta blockers or calcium channel blockers is allowed as long as the participant has been on a stable dose for at least 14 days prior to Screening
7. Has evidence of current abuse of drugs or alcohol or a history of abuse that, in the Investigator's opinion, would cause the participant to be noncompliant or would otherwise increase the risk to the participant
8. Is unable to comply with the study requirements, including the number of required visits to the clinical site

5.4. Screening and Enrollment

Eligible individuals who completed Study MYK-461-004 may be enrolled. An informed consent form (ICF) must be signed and dated by the participant before any study-specific tests or procedures may be performed.

If possible, each participant should keep his or her unique identification number that was assigned upon entry into Study MYK-461-004. Numbers do not include identifiable information. The identification number will be used to identify the participant throughout the study and should appear on all study-related documentation. Rescreening may be allowed at the discretion of the Investigator and the MyoKardia Medical Monitor.

5.5. Withdrawal of Participants

5.5.1. Withdrawal from the Study

The degree to which a study participant withdraws can vary. However, every effort should be made to collect important safety data if feasible and the study participant agrees. Study participants can:

- Withdraw from treatment (permanent treatment discontinuation) and agree to participate in the early termination (ET) and EOS visits
- Withdraw from treatment (permanent treatment discontinuation) and agree to participate in the ET visit
- Withdraw from treatment (permanent treatment discontinuation) and all follow-up

Participants may withdraw from the study before study completion if they decide to do so, at any time, for any reason. Withdrawal of consent for treatment (permanent treatment discontinuation) should be distinguished from withdrawal of consent for ongoing study participation with scheduled visits and from withdrawal of consent for non-participant contact follow-up (eg, medical records check).

If possible, and prior to the withdrawal of consent for ongoing study participation, the participants will be assessed using the procedures normally planned for the ET visit.

Participants who withdraw from the study should be explicitly asked about the reason and the contribution of any possible AE(s) that led to their decision, and all AE information elicited should be documented. The participant may withdraw consent verbally or in writing. If the consent is withdrawn verbally, the site should document it appropriately. Preferably, the participant should withdraw consent in writing and, if the participant or the participant's representative refuses or is physically unavailable, the site should document and sign the reason for the participant's failure to withdraw consent in writing.

All study withdrawals should be recorded by the Investigator in the appropriate electronic case report form (eCRF) and in the participant's medical records when considered as confirmed. The date of the withdrawal and the reason should be documented.

For participants who do not withdraw consent for ongoing study participation but fail to return to the site, the Investigator should make every effort to contact the participant (eg, contacting participant's family or private physician, reviewing available registries or health care databases) and to determine the participant's health status, particularly vital status. Attempts to contact such participants must be documented in the participant's records (eg, number of attempts and dates of attempted telephone contact and receipt for sending a registered letter).

Participants who have withdrawn from the study cannot be treated further in the study. Their study identification numbers must not be reused.

Treatment Discontinuation

The Investigator should discontinue a participant's study treatment permanently for any of the following reasons:

- Pregnancy

- Heart failure related to systolic dysfunction
- Study termination
- Study site termination by MyoKardia (eg, in the case of major, noncorrectable protocol deviations)
- Undergoing septal reduction therapy
- Participant withdrawal from treatment or withdrawal from study

Study treatment will be discontinued in the case of exaggerated pharmacologic effect (systolic dysfunction), higher than expected plasma concentration, or excessive QT prolongation (see [Section 7.5](#)).

In addition, study treatment may be temporarily discontinued in the case of an AE or SAE at the Investigator's discretion if there is a safety concern.

In all cases, the reason(s) for permanent treatment discontinuation or study withdrawal will be recorded in the source document and on the appropriate eCRF.

5.5.2. Handling of Participants After Permanent Treatment Discontinuation

After permanent discontinuation of treatment, participants will be followed according to the study procedures as specified in this protocol through the scheduled date of study completion, or through the recovery or stabilization of any AE to be followed as specified in this protocol, whichever comes last.

After permanent discontinuation of treatment, the participants will be assessed using the procedures planned for the ET and EOS visits.

6. RANDOMIZATION AND BLINDING PROCEDURES

6.1. Randomization

Participants will not be randomized to treatment in this study.

6.2. Study Blinding

Treatment will not be blinded in this study.

7. STUDY TREATMENT

All participants will receive mavacamten in an open-label manner.

7.1. Formulation, Packaging, and Labeling of Study Drug

Mavacamten presentation is size 2, blue opaque capsules printed with a yellow band on the body and black band on the cap. Each capsule contains white to off-white powder. The active capsules are supplied in 3 strengths: 5, 10, and 15 mg.

Mavacamten capsules have been manufactured according to current Good Manufacturing Practice (cGMP) regulations. They will be supplied in high-density polyethylene bottles with induction seals and child-resistant caps at 30 count per bottle. All study drug will be labeled according to applicable local regulatory guidelines.

Mavacamten capsules must be stored at 2°C to 25°C (36°F to 77°F) in the packaging supplied by MyoKardia. Study medication at the investigational site will be stored in a secure area with access limited to authorized study personnel.

7.2. Administration and Schedule of Study Drug

Study drug will be supplied to participants in 30-count high-density polyethylene bottles that are appropriately labeled. The participants will be instructed to store their supply of study drug capsules and bottles in a cool, dry place.

Participants will take study drug as directed by the Investigator. Participants should be instructed to take the study drug at approximately the same time every day (\pm 8 hours). Study drug should be taken with approximately 8 ounces of water. If the dosing window is missed, the participant should not take study drug that day. Participants should never take 2 doses of study drug within an 8-hour period. At Week 4, dosing should occur in the clinic after a blood draw for a plasma PK sample.

7.3. Treatment Compliance

Compliance with study drug will be monitored by capsule count at each clinic visit ([Table 2](#) and [Table 3](#)).

7.4. Hepatotoxicity Stopping and Rechallenge Rules

Participants with abnormal hepatic laboratory values (eg, alkaline phosphatase [ALP], AST, ALT, total bilirubin [TBL], or international normalized ratio) or signs/symptoms of hepatitis may meet the criteria for withholding study medication or other protocol-required therapies. Withholding is either permanent or conditional depending on the clinical circumstances discussed below (as specified in the [US Food and Drug Administration Guidance for Industry: Drug-Induced Liver Injury: Premarketing Clinical Evaluation, 2009](#)).

7.4.1. Criteria for Permanent Withholding of Mavacamten Due to Potential Hepatotoxicity

Mavacamten should be discontinued permanently and the participant should be followed according to the recommendations in [Appendix 3](#) for possible drug-induced liver injury (DILI) if all the criteria below are met:

- TBL > 2 × upper limit of normal (ULN) or international normalized ratio > 1.5
- AND increased AST or ALT if the baseline value was < ULN and AST or ALT elevation is > 3 × ULN
- AND no other cause for the combination of laboratory abnormalities is immediately apparent. Important potential causes for abnormal AST/ALT or TBL values include, but are not limited to, the following:

- Obstructive gall bladder or bile duct disease
- Viral or alcoholic hepatitis (eg, hepatitis A/B/C/D/E, Epstein-Barr virus, cytomegalovirus, herpes simplex virus, varicella)
- Hypoxic or ischemic hepatopathy or congestive hepatopathy in association with significant right-sided heart failure
- Concomitant administration of other hepatotoxins, including drugs that inhibit bilirubin glucuronidation (eg, indinavir, atazanavir, irinotecan) or herbal or dietary supplements
- Heritable disorders causing impaired glucuronidation (eg, Gilbert syndrome); α -1 antitrypsin deficiency
- Autoimmune hepatitis
- Nonalcoholic steatohepatitis or other fatty liver disease

If an alternative cause for hepatotoxicity is identified or less stringent conditions developed than what is noted above, the Investigator will determine whether study drug and other protocol-required therapies should be permanently or temporarily discontinued based on participant population and/or severity of the hepatotoxicity or event, as deemed appropriate for the safety of the participant.

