7.4.2. Criteria for Conditional Withholding of Mavacamten Due to Potential Hepatotoxicity

For participants who do not meet the criteria for permanent withholding of study medication outlined above, mavacamten should be withheld if ANY of the following criteria are met, and the participant should be evaluated for DILI:

- Elevation of either AST or ALT, regardless of baseline AST or ALT value, if:
 - $> 8 \times \text{ULN}$ at any time
 - $> 5 \times \text{ULN}$ and $< 8 \times \text{ULN}$ for ≥ 2 weeks
 - $> 5 \times \text{ULN}$ and $< 8 \times \text{ULN}$ and unable to adhere to enhanced monitoring schedule
- OR: clinical signs or symptoms that are, in the opinion of the Investigator, consistent with hepatitis (such as right upper quadrant pain/tenderness, fever, nausea, vomiting, jaundice, rash, or eosinophilia $> 5\%$). If such signs or symptoms are coupled with ALT or AST elevations $> 3 \times \text{ULN}$, study medication should be withheld
- OR: TBL $> 3 \times \text{ULN}$ at any time
- OR: ALP $> 8 \times \text{ULN}$ at any time

Mavacamten should be withheld pending an investigation into alternative causes of DILI. If study medication is withheld, the participant should be followed according to recommendations in [Appendix 3](#) for possible DILI. Rechallenge may be considered if an alternative cause, such as acute hepatitis B infection, is discovered and the laboratory abnormalities resolve to normal or baseline ([Section 7.4.3](#)).

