APPENDIX 3. POTENTIAL DRUG-INDUCED LIVER INJURY REPORTING AND ADDITIONAL ASSESSMENTS REPORTING

To facilitate appropriate monitoring for signals of drug-induced liver injury (DILI), cases of concurrent aspartate/alanine aminotransferase (AST/ALT) and total bilirubin (TBL) elevation according to the criteria specified in [Section 7.4](#) ($3 \times$ upper limit of normal [ULN] for AST/ALT and $2 \times$ ULN for TBL in participants with no underlying liver disease and eligibility criteria requiring normal liver function at baseline) require the following:

- The event is to be reported to MyoKardia as a serious adverse event (SAE) within 24 hours of discovery or notification of the event (ie, before additional etiologic investigations have been concluded)
- The appropriate case report form (CRF) (eg, Adverse Event CRF) that captures information necessary to facilitate the evaluation of treatment-emergent liver abnormalities are to be completed and sent to MyoKardia

Other events of hepatotoxicity and potential DILI are to be reported as SAEs if they meet the criteria for an SAE defined in [Section 10.1.3](#).

Additional Clinical Assessments and Observation

All participants for whom investigational product(s) or protocol-required therapies is/are withheld (either permanently or conditionally) due to potential DILI or who experience AST/ALT elevations $> 3 \times$ ULN are to undergo a period of “close observation” until abnormalities return to normal or to the participant’s baseline levels. Assessments that are to be performed during this period include the following:

- Repeat liver chemistries within 24-48 hours (ALT, AST, alkaline phosphatase [ALP], TBL); in cases of TBL $> 2 \times$ ULN or AST/ALT much greater than $3 \times$ ULN, retesting is to be performed within 24 hours.
 - For participants that are far away from the trial site, it may be difficult for the participants to return to the trial site promptly. In this case, the participants should be retested locally, but normal laboratory ranges should be recorded, results should be made available to trial Investigators immediately, and the data should be included in the case reports.
 - Participants are to be monitored at least twice weekly; testing frequency may decrease to once per week or less if laboratory abnormalities stabilize or the investigational product(s) or protocol-required therapies have been discontinued AND the participant is asymptomatic.

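### Section 7.4.1 words the permanent liver stop only for AST/ALT below ULN at baseline although raised baselines are eligible, and the normalization table in 11.3.8.3 has no place for recovery on drug or after temporary withholding

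*Combined protocol and SAP*

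**What the plan says.** **Stopping rules.** Section 7.4.1 makes discontinuation permanent only when every listed criterion is met: TBL above 2 × ULN or INR above 1.5; the transaminase criterion, "AND increased AST or ALT if the baseline value was < ULN and AST or ALT elevation is > 3 × ULN"; and no other evident cause. If another cause is found, or the picture is milder, "the Investigator will determine whether study drug and other protocol-required therapies should be permanently or temporarily discontinued".

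**Eligibility.** Inclusion criterion 4 (Section 5.2) says that "a participant with safety laboratory parameters outside normal limits may be included if he or she meets all of the following criteria". One condition is that the abnormality is judged clinically unimportant. The transaminase condition begins "If there is an alanine aminotransferase (ALT) or aspartate aminotransferase (AST) result, the value must be" and sets the ceiling at below 3 × the upper reference limit.

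**Conditional withholding.** Section 7.4.2 opens with "Elevation of either AST or ALT, regardless of baseline AST or ALT value". It withholds drug above 8 × ULN, and between 5 and 8 × ULN if this lasts 2 weeks or more or enhanced monitoring is not possible. TBL above 3 × ULN, ALP above 8 × ULN and signs of hepatitis also count. On the signs it adds: "If such signs or symptoms are coupled with ALT or AST elevations" above 3 × ULN, drug should be withheld. Rechallenge may be considered when an alternative cause "is discovered and the laboratory abnormalities resolve to normal or baseline". Section 7.4.3 bars rechallenge for those who clearly meet 7.4.1.

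**Reporting.** Appendix 3 requires a 24-hour SAE report for concurrent AST/ALT (3 × ULN) and TBL (2 × ULN) elevation "in participants with no underlying liver disease and eligibility criteria requiring normal liver function at baseline".

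**Analysis.** Section 11.3.8.3 summarizes normalization of liver tests, counting return to baseline where baseline exceeded ULN. It names two outcomes: no normalization, and normalization once drug has been permanently stopped.

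**The concern.** The protocol enrols people whose transaminases may already be at or above ULN, but its strictest liver rule gives a limit only for those who start below ULN. Three consequences hang on that clause or on the matching Appendix 3 premise: the permanent stop, the bar on rechallenge and the automatic SAE report. If the clause is read literally, identical on-study results lead to a mandatory stop in one participant and to Investigator judgment in another, and the protocol gives no reason for the difference.

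The second issue is separate. The normalization table should show whether an elevation resolved, and under what dosing. As listed, a participant who recovers while still taking mavacamten, or during a temporary hold, fits neither outcome. Such cases would be left out or misfiled, in a study whose primary objective is long-term safety and tolerability.

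**Working it through.** The plan gives no figure to reproduce. This is a check of rule logic, in multiples of ULN.

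**1. Two readings of the 7.4.1 transaminase criterion**
- Literal: baseline < 1 and on-study value > 3.
- Baseline-neutral: on-study value > 3 for everyone, with the baseline phrase qualifying only what counts as increased.

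The wording permits both. The explicit baseline-neutral phrase in 7.4.2 lends some weight to the literal reading of 7.4.1, since that wording was available and not used.

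**2. Same on-study values, two baselines**

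Take AST = ALT = 4.5, TBL = 2.2, ALP normal, no hepatitis signs, no other cause.
- Baseline AST and ALT 0.9: 4.5 > 3 and 2.2 > 2, so permanent stop on both readings.
- Baseline AST and ALT 1.5 (eligible, because 1.5 < 3): permanent stop on the baseline-neutral reading. On the literal reading the criterion fails because 1.5 is not below 1. Section 7.4.2 does not fire either: 4.5 is not above 5, 2.2 is not above 3, ALP is normal and there are no signs.

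Replacing the bilirubin finding with INR 1.6 gives the same result, so the gap does not depend on raised bilirubin. Adding jaundice to the first case, or other hepatitis signs to the INR case, makes withholding mandatory under 7.4.2. If either enzyme was below ULN at baseline, both readings stop the drug here.

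**3. Edges of the uncovered region (literal reading, both enzymes ≥ 1 at baseline)**
- AST/ALT above 3 and up to 5, or above 5 and below 8 for under 2 weeks with monitoring in place.
- TBL above 2 and up to 3, or INR above 1.5 with TBL not above 3.
- ALP not above 8, no hepatitis signs, no other cause.

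**4. What is lost there**
- The mandatory permanent stop (7.4.1).
- The rechallenge bar, because 7.4.3 ties it to clearly meeting 7.4.1.
- For the bilirubin pattern, the automatic SAE report. Appendix 3 states that trigger under a normal-baseline premise that Section 5.2 does not support, whichever way 7.4.1 is read.

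**5. What a limit of 3 × ULN at any baseline would mean**

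Fold rise needed = 3 / baseline: 3/1.0 = 3.0; 3/1.5 = 2.0; 3/2.0 = 1.5; 3/2.9 = 1.03. A move from 2.9 to 3.1 is 3.1/2.9 − 1 = 0.069, about 7%.

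As an assumed illustration, not from the documents, require both > 3 and > 2 × baseline. The limit is max(3, 2 × baseline): 3.0 at 1.5, 4.0 at 2.0, 5.8 at 2.9. This avoids the stop at 3.1 for someone entering at 2.9, but it also leaves 4.5 in that person to judgment.

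**6. Normalization outcomes in 11.3.8.3**
- Never normalized: has a category.
- Normalized after permanent discontinuation: has a category.
- Normalized on continued drug: none.
- Normalized after temporary withholding: none.

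The third outcome is the default route for isolated AST/ALT up to 5 without signs, where neither 7.4.1 nor 7.4.2 mandates withholding; the lowest elevation band in 11.3.8.3 is 1–3. The fourth is foreseen in 7.4.2. Above 8, drug should be withheld, so recovery on drug is not expected in the bands above 10.

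**The case against.** The strongest reply is that 7.4.1 is clumsily worded, not defective: on the baseline-neutral reading there is no stopping gap at all. Even on the literal reading the safeguards are real. The Investigator may stop drug permanently. Section 7.4.2 applies at any baseline. Appendix 3 requires close observation for any AST/ALT above 3 × ULN, with a retest within 24 hours when TBL exceeds 2 × ULN, at least twice-weekly monitoring at first and a specialist consult. Ordinary SAE criteria (10.1.3) still apply, and rechallenge needs unanimous Investigator and Sponsor agreement. If the raised baseline itself has one of the causes listed in 7.4.1, the third criterion may fail on either reading. Leaving raised baselines to judgment is also a defensible clinical choice.

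Most of this stands, and it limits the size of the point. It does not remove it. A mandatory stop should not depend on how a bullet is parsed, and if discretion is intended the text should say so. The Appendix 3 premise conflicts with Section 5.2 on any reading.

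On the table, one may reply that out-of-range listings are produced, that Section 11.3 calls itself an outline, and that with row totals the participants in neither category can be found by subtraction. That holds only if totals are shown and nobody is misfiled as never normalized. The split between recovery on drug and after a temporary hold is lost in any case. A separate analysis document, not among those reviewed, could contain fuller categories.

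**Conclusion.** Both parts hold, within limits, and should be corrected.

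Part 1 is an ambiguity in a mandatory safety rule together with a wrong premise in Appendix 3. It bites only on the literal reading, for participants with both enzymes at or above ULN at baseline, inside the region set out above. The number affected is unknown and probably small: enrolment is capped at 20, and abnormal entry values must be judged clinically unimportant. If nobody enters with raised values, the rule gap has no practical effect.

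A reader might infer that participants with raised baselines have no liver protection. The documents do not support that: conditional withholding, Investigator discretion and close observation all remain. A reader might also count example laboratory profiles, or empty table cells, to express the size. Profiles picked from inside the region merely restate the two readings. A cell count would include on-drug recovery at levels where 7.4.2 requires withholding, and could overlook the ALP and TBL categories.

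Part 2 affects descriptive safety reporting only. No hypothesis test, sample size or stopping decision depends on it.

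**What to change.** 1. **Appendix 3.** Delete the normal-baseline premise, so that concurrent AST/ALT above 3 × ULN and TBL above 2 × ULN is reported as an SAE within 24 hours at any baseline.
2. **Section 7.4.1.** State the limit for baseline at or above ULN. The default is AST or ALT above 3 × ULN regardless of baseline. The medical team may prefer a multiple of baseline, or explicit discretion, provided it is written down.
3. **Section 11.3.8.3.** Use four outcomes: normalized on treatment; normalized after temporary withholding; normalized after permanent discontinuation; never normalized.

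The cost is amendment wording and two more table categories, with no new procedures. The clinical downside of the default is that someone entering near 3 × ULN could be stopped permanently after a rise of about 7% (2.9 to 3.1 × ULN), though only if TBL or INR is also raised and no other cause is evident. A baseline multiple avoids that, at the price of leaving some larger rises to judgment.
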